## PROTOCOL SYNOPSIS

**PROTOCOL NO.:** SIGA-246-022

**TITLE:** A Post Marketing Study of the Safety, Tolerability, and Pharmacokinetics of TPOXX® in Adult Subjects Weighing More Than 120 kg

**STUDY PHASE:** 4 Post Marketing Study

**STUDY SITE:** PPD Phase I Clinic, [name].

### OBJECTIVES:

#### Primary:

The primary objective of this study is to determine the pharmacokinetic (PK) profile of 600 mg oral TPOXX (3 × 200-mg capsules) administered twice daily (BID) for 7 days in adult subjects weighing more than 120 kg to determine if a change in dosing regimen would be needed in these patients.

#### Secondary:

The secondary objective of this study is to evaluate the safety and tolerability of 600 mg oral TPOXX administered BID for 7 days in healthy adult subjects weighing more than 120 kg.

### STUDY DESIGN AND METHODOLOGY:

This is an open-label, multiple-dose study to assess the safety, tolerability, and PK of TPOXX 600 mg BID when administered orally for 7 days to adult subjects weighing more than 120 kg. A total of 36 subjects, ages 18 to 50, inclusive, will be enrolled. The study will consist of a screening period (Day -28 to Day -2), a treatment and confinement period (Days -1 to 9), a follow-up telephone call or visit (Day 14 [+2 days]), and a follow-up telephone call (Day 37 [+2 days]).

Subjects will undergo screening evaluations to determine eligibility within 28 days before study drug administration. Subjects will be admitted to the study site on Day -1 to complete baseline assessments; results of these assessments must be reviewed by the investigator before dosing. Starting in the morning of Day 1, subjects will receive 600 mg oral TPOXX BID for 7 days (Days 1 through 7).

All subjects will be provided meals (consisting of approximately 600 calories and 25 g fat) 30 minutes prior to study drug administration and subjects must fast for 2 hours after taking study drug. Subjects should eat this meal within 30 minutes or less of taking study drug. Study drug and meals must be taken with water only, and no other beverage except water should be ingested within 3 hours before or 3 hours after study drug administration.

Subjects will remain confined to the study site for collection of PK samples and will be carefully monitored for safety and tolerability until discharge on Day 9. Subjects who have abnormal physical examination findings or an ongoing adverse event (AE)/serious adverse event (SAE) on Day 9 that is deemed related to study drug or per investigator or SIGA discretion will return to the study site on Day 14 (+2 days) for a follow-up visit. All other subjects will have the Day 14 (+2 days) follow-up via telephone. All subjects will have a

follow-up telephone call 30 days after administration of the last dose of study drug (Day 37 [+2 days]) to report any SAEs. At the time of discharge from the clinical research unit, subjects will be instructed to notify the investigator of any SAEs that occur within 30 days after administration of the last dose of study drug. Serious AEs will be followed until the SAE is stable or until resolution as determined by the investigator and/or medical monitor.

The total duration of the study for each subject, including the screening period, treatment period, and the Day 37 (+2 days) follow-up telephone call, will be approximately 65 days.

### **STUDY POPULATION:**

#### **Inclusion Criteria:**

Each subject must meet all the following criteria to be enrolled in this study:

1. Subject is male or female between 18 and 50 years of age, inclusive.
2. Subject has a body weight >120 kg at screening, at check-in on Day -1, and prior to dosing on Day 1.
3. Women of childbearing potential, have a negative  $\beta$  human chorionic gonadotropin pregnancy test (serum) at the screening visit and a confirmatory negative serum pregnancy test on Day -1 before receipt of study drug, and meet 1 of the following criteria:
  - a. The subject or their partner has undergone surgical sterilization
  - b. The subject is postmenopausal, defined as 12 consecutive months with no menses without an alternative medical cause and has a documented plasma follicle-stimulating hormone level >40 IU/mL
  - c. The subject agrees to be abstinent (ie, heterosexually inactive or women in a religious order)
  - d. The subject agrees to consistently use 1 of the following methods of contraception from the beginning of screening (which they had been consistently using for at least 30 days before the first dose of study drug) through 30 days after the last dose of study drug:
    - i. Condoms, male or female, with a spermicide  
**NOTE:** For male subjects, condoms must be used for 90 days after the last dose of study drug.
    - ii. Diaphragm or cervical cap with spermicide
    - iii. Intrauterine device with spermicide
    - iv. Oral contraceptives or other hormonal methods  
**NOTE:** Subject must agree to use an additional nonhormonal method of contraception in conjunction with oral contraceptives.
    - v. Male sexual partner who had undergone a vasectomy at least 3 months before screening
4. Male subjects must agree to not donate sperm from the first dose of study drug through 90 days after the last dose of study drug.

5. Subject is considered by the investigator to be in good general health as determined by medical history (no hospitalizations for chronic medical conditions in the previous 2 years), clinical laboratory results, vital sign measurements, 12-lead electrocardiogram (ECG) results, and physical examination findings at screening.
6. Subject agrees to comply with all protocol requirements.
7. Subject is able to provide written informed consent.
8. Subject agrees to comply with the dietary requirements.
9. Subject does not intend to lose weight (diet or weight loss) from the screening visit and throughout the study.

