### **3.1 INCLUSION CRITERIA**

Each subject must meet all the following criteria to be enrolled in this study:

1. Subject is male or female between 18 and 50 years of age, inclusive.
2. Subject has a body weight >120 kg at screening, at check-in on Day -1, and prior to dosing on Day 1.
3. Women of childbearing potential, have a negative  $\beta$  human chorionic gonadotropin pregnancy test (serum) at the screening visit and a confirmatory negative serum

- pregnancy test on Day –1 before receipt of study drug, and meet 1 of the following criteria:
- a. The subject or their partner has undergone surgical sterilization
  - b. The subject is postmenopausal, defined as 12 consecutive months with no menses without an alternative medical cause and has a documented plasma follicle-stimulating hormone level  $>40$  IU/mL
  - c. The subject agrees to be abstinent (ie, heterosexually inactive or women in a religious order)
  - d. The subject agrees to consistently use 1 of the following methods of contraception from the beginning of screening (which they had been consistently using for at least 30 days before the first dose of study drug) through 30 days after the last dose of study drug:
    - i. Condoms, male or female, with a spermicide  
**NOTE:** For male subjects, condoms must be used for 90 days after the last dose of study drug.
    - ii. Diaphragm or cervical cap with spermicide
    - iii. Intrauterine device with spermicide
    - iv. Oral contraceptives or other hormonal methods  
**NOTE:** Subject must agree to use an additional nonhormonal method of contraception in conjunction with oral contraceptives.
    - v. Male sexual partner who had undergone a vasectomy at least 3 months before screening.
  4. Male subjects must agree to not donate sperm from the first dose of study drug through 90 days after the last dose of study drug.
  5. Subject is considered by the investigator to be in good general health as determined by medical history (no hospitalizations for chronic medical conditions in the previous 2 years), clinical laboratory results, vital sign measurements, 12-lead ECG results, and physical examination findings at screening.
  6. Subject agrees to comply with all protocol requirements.
  7. Subject is able to provide written informed consent.
  8. Subject agrees to comply with the dietary requirements.

9. Subject does not intend to lose weight (diet or weight loss) from the screening visit and throughout the study.

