## 6.2.2 Clinical Laboratory Testing

Clinical laboratory tests will be performed by the PPD Central Laboratory. Blood samples will be collected at the time points indicated in the schedule of events (Table 9-1) and will be prepared using standard procedures.

Repeat clinical laboratory tests may be performed at the discretion of the investigator, if necessary, to evaluate inclusion and exclusion criteria or clinical laboratory abnormalities. PPD central laboratory will provide the reference ranges for all clinical laboratory safety parameters.

The following clinical laboratory assessments will be performed:

Hematology	Hematocrit, hemoglobin, mean corpuscular hemoglobin, mean corpuscular hemoglobin concentration, total and differential leukocyte count (basophils, eosinophils, lymphocytes, monocytes, neutrophils), mean corpuscular volume, platelet count, red blood cell count, and red cell distribution width
Serum Chemistry	Alanine aminotransferase, albumin, alkaline phosphatase, anion gap, aspartate aminotransferase, bilirubin (total), blood urea nitrogen, calcium, carbon dioxide, chloride, creatinine clearance (calculated a ), gamma-glutamyltransferase, globulin, glucose, lactate dehydrogenase, phosphorus, potassium, sodium, total protein, and uric acid

Urinalysis                      Appearance, bilirubin, blood, color, glucose, ketones, leukocytes, microscopy (performed if dipstick is  $\geq 1+$ ; includes bacteria, cast, crystals, epithelial cells, red blood cells, and white blood cells), nitrates, pH, protein, specific gravity, turbidity, and urobilinogen

a Creatinine clearance (CLcr) will be calculated using the Cockcroft-Gault formula:

$$CLcr (mL/min) = \frac{[140 - age(years)] \times weight (kg)}{72 \times serum\ creatinine (mg/dL)} \{ \times 0.85 \text{ if female} \}$$

Glycosylated hemoglobin A1c and a fasting lipid panel including cholesterol (total, high-density lipoprotein, calculated low-density lipoprotein, and triglycerides) will be performed at screening.

Serum pregnancy test ( $\beta$  human chorionic gonadotropin) for women of childbearing potential will be performed at screening and on Day -1.

A serum follicle-stimulating hormone test for postmenopausal women will be performed at screening.

Human immunodeficiency virus (type 1 and 2) antibodies, hepatitis B surface antigen, and hepatitis C virus antibody will be assessed at screening only.

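### The FSH limit in inclusion criterion 3b is written as >40 IU/mL, apparently about 1000-fold too high, so the postmenopausal option cannot be met as written

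*Protocol*

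**What the plan says.** Inclusion criterion 3 applies to women of childbearing potential. Besides negative pregnancy tests, it asks them to "meet 1 of the following criteria", listed as options a to d. Option b reads: "The subject is postmenopausal, defined as 12 consecutive months with no menses without an alternative medical cause", and it adds a hormone requirement, that the subject "has a documented plasma follicle-stimulating hormone level >40 IU/mL". The two parts are joined by 'and', so absence of menses alone does not satisfy the option.

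Section 3.1 repeats the criterion with the same number and the same unit. Section 6.2.2 provides the test: "A serum follicle-stimulating hormone test for postmenopausal women will be performed at screening". Note (p) to the schedule of events says the same. Neither place gives a unit or a reference range. Neither amendment in the change history (Section 9.4) touches this criterion.

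**The concern.** The limit appears to carry the wrong unit. A number such as 40 is plausible in mIU/mL, which is the same as IU/L. In IU/mL it is one thousand times larger and seems to lie far beyond any level a subject could have.

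This is a limit the site must apply to a laboratory result before enrolment. Followed literally, it makes option 3b empty, and the hormone test ordered at screening can never confirm eligibility. A postmenopausal woman would then have to qualify through sterilization, abstinence or contraception, or be excluded. If the site instead reads the limit in whatever unit the laboratory reports, it enrols her against the written criterion. Section 9.3.6.2.2 names failure to adhere to eligibility criteria as something an important deviation can include, and Sections 9.3.1 and 9.3.3.1.1 call for 100% source verification, so a monitor could well notice the mismatch.

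**Working it through.** **Inputs from the protocol**

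- Limit: >40 IU/mL, in the Synopsis (criterion 3b) and Section 3.1 (criterion 3b).
- Structure: 12 months without menses and the hormone level are both required within 3b; one of a to d is enough for criterion 3.
- Age: "Subject is male or female between 18 and 50 years of age, inclusive".
- Test: serum, at screening, with no unit or range stated (Section 6.2.2).

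The protocol does not derive the limit, so there is no figure of its own to reproduce. The check is a unit conversion.

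**Conversion**

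1 IU/mL = 1000 mIU/mL = 1000 IU/L, so

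40 IU/mL × 1000 mL/L = 40,000 IU/L = 40,000 mIU/mL.

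The same number in mIU/mL would be 40 / 1000 = 0.04 IU/mL, exactly 1000-fold lower.

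**Comparison with plausible levels**

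The protocol gives no physiological range, so one has to be assumed. The base assumption is 25 to 200 IU/L after menopause; 20 to 300 IU/L is shown as a deliberately wider range. The ratio is 40,000 divided by the assumed level.

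| Assumed level (IU/L = mIU/mL) | In IU/mL | Written limit ÷ level |
|---|---|---|
| 20 | 0.02 | 2000 |
| 25 | 0.025 | 1600 |
| 40 | 0.04 | 1000 |
| 100 | 0.1 | 400 |
| 200 | 0.2 | 200 |
| 300 | 0.3 | 133 |

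No level in either range passes the written limit. The conclusion would fail only if real levels exceeded 40,000 IU/L, which is 133 times the top of the wider range.

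**Could this be a slip in reading the PDF?** That is unlikely. The Synopsis and Section 3.1 are separate copies of the criterion, and both carry the same number and unit.

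**Specimen type.** Criterion 3b names plasma; Section 6.2.2 and schedule note (p) name serum. No eligibility decision is shown to turn on this.

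**The case against.** The best case against the point is that the protocol does not contradict itself on the limit: both copies agree, and nothing in the document shows what level to expect. Calling the limit too high needs a range from outside. That is true, and it is why the intended unit is an inference and the range is labelled as an assumption. The conclusion does not depend on its exact ends, because the margin is still more than a hundredfold at the extreme.

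The second argument is that little harm follows, and this largely stands. Options 3a, 3c and 3d remain available. The error is restrictive: it closes a route and admits nobody who should be kept out. With an age cap of 50 and 36 subjects of both sexes, few women would rely on 3b, although the protocol gives no count. A site would probably read the result in its laboratory's customary unit, and enrolling a truly postmenopausal woman that way would hardly affect safety or data reliability, which are the tests Section 9.3.6.2.2 sets for an important deviation. Still, that section expressly says eligibility breaches can be counted, and a criterion that works only when misread should be corrected.

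The difference between plasma and serum is clerical and adds no weight.

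**Conclusion.** The concern holds. As written, the limit equals 40,000 IU/L, 200 to 1600 times the assumed postmenopausal range of 25 to 200 IU/L and 133 to 2000 times the wider range of 20 to 300 IU/L. Under either assumption, no woman can qualify through option 3b. That mIU/mL (equivalently IU/L) was meant is likely but not stated in the protocol.

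The importance is low. One of four alternative routes is closed, few subjects are likely to need it, and the sample size, analysis populations, pharmacokinetic parameters and safety analyses are unaffected. The point is worth correcting because it is an operative eligibility limit, and leaving it invites either needless exclusion or an avoidable deviation.

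**What to change.** Check the unit of the follicle-stimulating hormone limit against the unit in which the central laboratory reports the test, and correct it in criterion 3b in both the Synopsis and Section 3.1. In the same edit, name one specimen type throughout criterion 3b, Section 6.2.2 and schedule note (p).

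The cost is a unit correction in two places and one aligned term. No analysis, sample size or visit changes.

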### **1.3 POTENTIAL RISKS AND BENEFITS**

#### **1.3.1 Potential Risks**

The effect of TPOXX on a fetus or nursing baby is not yet known; therefore, women of childbearing potential participating in this study will be required to agree to use an acceptable means of birth control from 30 days before the first dose of study drug and continuing through 30 days after the last dose of study drug. Pregnancy testing will be performed at the screening visit and checked by the investigator for negative pregnancy before administration of study drug on Day -1. Women who are pregnant or lactating or plan to become pregnant within 3 months after study drug administration will be excluded from the study; if a female subject becomes pregnant during study participation, study drug dosing will be discontinued, and the subject will be withdrawn from the study (Section 6.2.1.9).

As with all drugs, there is potential risk of an allergic reaction. At this time, there is no definitive information on the allergic activity of TPOXX. Headache and nausea have been the most common AEs in clinical studies completed to date. There may be other side effects

of TPOXX that are not yet known. Full details can be found in the TPOXX full prescribing information.

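### Inclusion criterion 3c accepts an agreement to be abstinent with no stated period, so the eligibility text does not carry the 30-day pre-dose and post-dose window set in Section 1.3.1 and in 3d

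*Protocol*

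**What the plan says.** Section 1.3.1 notes that the effect of the drug on a fetus is unknown. For that reason it has women of childbearing potential agree to "birth control from 30 days before the first dose of study drug and continuing through 30 days after the last dose of study drug". It makes no separate provision for abstinence.

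Inclusion criterion 3, worded alike in the synopsis and in Section 3.1, asks these women for a negative serum pregnancy test at screening and "a confirmatory negative serum pregnancy test on Day -1 before receipt of study drug". They must also "meet 1 of the following criteria", namely 3a to 3d:

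- 3d (contraceptive methods) carries the window of Section 1.3.1. The method must be one "which they had been consistently using for at least 30 days before the first dose of study drug) through 30 days after the last dose".
- 3c (abstinence) carries none: "The subject agrees to be abstinent (ie, heterosexually inactive or women in a religious order".

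On timing, the synopsis and Section 4 state: "The study will consist of a screening period (Day -28 to Day -2", followed by confinement from Day -1 to Day 9 and dosing on Days 1 to 7. Section 6.2.2 lists serum pregnancy tests at screening and on Day -1, and no later one.

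**The concern.** A site enrols against the numbered criteria. A woman whose abstinence starts at screening can satisfy criterion 3 through 3c and still fall short of the pre-dose period that Section 1.3.1 gives as the safety condition. The gap matters because the protocol's own reason for the rule is that fetal effects are unknown.

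The omission also stands out against the drafting around it. 3a describes a completed state, 3b has a 12-month look-back, 3d has a period at both ends, and 3d(v) counts back 3 months from screening. Among the other undertakings, inclusion 4 (sperm donation) and inclusion 9 (weight loss) both state the period they cover. Of options 3a to 3d, only 3c is an undertaking without dates.

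**Working it through.** The plan gives no figure of its own to reproduce. The check compares the texts and counts days.

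**Inputs**

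- Pre-dose period: 30 days (Section 1.3.1; 3d).
- Post-dose period: 30 days (same places).
- Screening: Day -28 to Day -2. Confinement: Day -1 to Day 9. Last dose: Day 7 (synopsis; Section 4).
- Serum pregnancy tests: at screening and on Day -1 (criterion 3; Section 6.2.2).
- Day numbering: no Day 0. This is an assumption, but it fits the plan's own figures: 28 + 37 = 65 days in total, and 7 + 30 = Day 37 for the last call.

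**Step 1: texts side by side**

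| Place | Start of the period | End of the period |
|---|---|---|
| Section 1.3.1 | 30 days before first dose | 30 days after last dose |
| Criterion 3d | in use at least 30 days before first dose | 30 days after last dose |
| Criterion 3c | not stated | not stated |

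**Step 2: pre-dose days covered under the literal reading of 3c**

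Let screening fall on Day -s and let abstinence begin that day. Days covered before Day 1 = s. Days uncovered = 30 - s. Days between the two pregnancy tests = s - 1.

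| Screening | Covered | Uncovered | Days between tests |
|---|---|---|---|
| Day -28 | 28 | 30 - 28 = 2 | 28 - 1 = 27 |
| Day -14 | 14 | 30 - 14 = 16 | 14 - 1 = 13 |
| Day -2 | 2 | 30 - 2 = 28 | 2 - 1 = 1 |

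**Step 3: when the tests fail to close the gap**

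Let L be the days from last intercourse until a resulting pregnancy shows on the serum test. The documents give no value for L. If intercourse last took place just before screening, the Day -1 test comes about s - 1 days later, so a pregnancy could escape both tests only if L exceeds s - 1. At Day -28 that needs L above 27 days; at Day -2 it needs only L above 1 day. The weakness therefore lies with late screening, whatever exact value L takes.

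**Step 4: post-dose days**

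The period runs from Day 8 to Day 37, which is 30 days. Confinement covers Days 8 and 9. The remaining 37 - 9 = 28 days rest on the woman's agreement, for which 3c gives no end but Section 1.3.1 does.

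**The case against.** The strongest reply is that 3c is silent rather than in conflict. Section 1.3.1 states a general rule for all women of childbearing potential, and inclusion 6 has each subject agree to follow every protocol requirement. The parenthesis in 3c also describes a way of life, so a site could refuse to call a woman with very recent intercourse heterosexually inactive. Two negative serum tests are required, and confinement limits exposure during dosing.

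Much of this stands. The intended window can be inferred, the parenthesis may denote an existing state, and the tests narrow the problem to very recent conceptions. What does not stand is that the gap is thereby closed. Inclusion 6 is a forward-looking agreement and cannot supply days already past. The parenthesis sets no duration. Confinement begins on Day -1, after the days in question.

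Two stronger readings are tempting, and the documents support neither:

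- A reader might infer that nothing binds an abstinent woman after discharge on Day 9. An undated agreement does not lapse at discharge. Section 1.3.1 runs to 30 days after the last dose, Section 6.2.1.9 requires counselling on avoiding pregnancy during participation, and exclusion 1 bars women planning pregnancy within 3 months after the last dose.
- A reader might infer that the 30-day look-back was set to cover the period in which the test cannot detect a pregnancy, and that 3c defeats that purpose. No section says so, and the detection interval is not in the documents.

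**Conclusion.** The point holds as a gap between the eligibility criterion and the safety section it should implement. Taken literally, 3c can admit a woman with 2 to 28 of the 30 pre-dose days uncovered. With late screening the second serum test adds little for a very recent conception.

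The result rests on two assumptions: that there is no Day 0, and that abstinence may begin at screening, which the wording of 3c allows but does not compel. The range of 2 to 28 is a count of calendar days, not a risk of pregnancy. The plan does not say how many women would qualify through 3c, but in a study of 36 men and women the number is likely small. The post-dose side is a matter of clarity only.

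This is a clarification of modest weight. It is worth making because it concerns subject safety, but it bears on neither the sample size nor the pharmacokinetic analysis.

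**What to change.** Reconcile criterion 3c, in both the synopsis and Section 3.1, with Section 1.3.1 and criterion 3d, so that the criterion itself states the period before the first dose and after the last dose that abstinence must cover. The sponsor should choose that period. If it is meant to differ from the one in Section 1.3.1, that section should say so.

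The cost is about one sentence in two places and no new procedure. A few women may become ineligible or need re-screening. If the chosen look-back is longer than the 28-day screening window, deferring Day 1 within that window cannot satisfy it for a woman whose abstinence starts at screening: even at Day -28 she reaches only 28 days, which is 2 short of 30.
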